## **2.8.4 Other safety data**

### **2.8.4.1 ECG and cardiac imaging data**

All ECG data at Screening Visit 2 will be listed by treatment group and patient, and abnormalities will be flagged.

### **2.8.4.2 Vital signs**

All vital signs data will be listed by treatment group, patient, and visit. Descriptive summary statistics will be provided by treatment and visit.

The number and percentage of subjects with newly occurring notable vital signs will be presented. Criteria for notable vital sign abnormalities are provided in [Table 2-5](#) below.

**Table 2-5 Criteria for notable vital sign abnormalities**

Vital sign (unit)	Notable abnormalities
Systolic blood pressure (mmHg)	>= 140 mmHg (hypertension) or < 90 mmHg (hypotension)
Diastolic blood pressure (mmHg)	>=90 mmHg (hypertension) or <60 mmHg (hypotension)
Pulse (bpm)	> 100 bpm (tachycardia) or <60 bpm (bradycardia)

Vital signs will be assessed at Screening Visit 2, 3, 4, 5, 6, 7, 8, 9, 10, 11, 12, 13, 14, 15, 16, 17, 18 and 19 and will include systolic and diastolic blood pressure, pulse rate and body temperature measurements.

## 2.9 Pharmacokinetic endpoints

Not applicable.

## 2.10 PD and PK/PD analyses

Not applicable.

## 2.11 Patient-reported outcomes

In this section, the details of each PRO is provided. The analysis of the PROs are presented in [Section 2.7](#).

### 2.11.1 ASDAS and ASDAS response categories

The Ankylosing Spondylitis Disease Activity Score (ASDAS) is a composite index to assess disease activity in AS. The ASDAS-CRP (Ankylosing Spondylitis Disease Activity Score) will be utilized to assess the disease activity status. Parameters used for the ASDAS calculation include spinal pain (BASDAI question 2), the patient's global assessment of disease activity, peripheral pain/swelling (BASDAI question 3), duration of morning stiffness (BASDAI question 6) and C-reactive protein (CRP) in mg/L ([Sieper 2009](#), [Lukas 2009](#)).

ASDAS-CRP is calculated in the following way:

$$\text{ASDAS-CRP} = 0.12 * \text{Back pain} + 0.06 * \text{Duration of Morning Stiffness} + 0.11 * \text{Patient Global} + 0.07 * \text{Peripheral Pain/Swelling} + 0.58 * \text{Ln}(\text{CRP}+1)$$

Disease activity states are inactive disease, moderate disease activity, high disease activity, and very high disease activity. The 3 values selected to separate these states were:

- < 1.3 between inactive disease and moderate disease activity,
- < 2.1 between moderate disease activity and high disease activity, and

- 3.5 between high disease activity and very high disease activity.

Selected cutoffs for improvement scores were a change  $\geq 1.1$  unit for “clinically important improvement” and a change  $\geq 2.0$  units for “major improvement” ([Machado 2011](#)).

### **2.11.2 Assessment of Spondylo-Arthritis International Society criteria (ASAS)**

The ASAS response measures consist of the following assessment domains (Sieper 2009).

ASAS domains:

1. Patient’s global assessment of disease activity measured on a numeric rating scale (NRS)
2. Patient’s assessment of back pain, represented by either total or nocturnal pain scores, both measured on a NRS (for derivation of response “back pain at any time” will be used from data)
3. Function represented by BASFI average of 10 questions regarding ability to perform specific tasks as measured by a NRS
4. Inflammation represented by mean duration and severity of morning stiffness, represented by the average of the last 2 questions on the 6-question BASDAI as measured by a NRS

#### **ASAS20**

ASAS 20 response is defined as an improvement of  $\geq 20\%$  and  $\geq 1$  unit on a scale of 10 in at least three of the four domains and no worsening of  $\geq 20\%$  and  $\geq 1$  unit on a scale of 10 in the remaining domain. Assessments will be made relative to patient’s baseline values.

#### **ASAS40**

ASAS 40 response is defined as an improvement of  $\geq 40\%$  and  $\geq 2$  units on a scale of 10 in at least three of the four domains and no worsening at all in the remaining domain. Assessments will be made relative to patient’s baseline values.

#### **ASAS partial remission**

The ASAS partial remission criteria is defined as a value not above 2 units in each of the domains 1 to 4 on a scale of 10.

[REDACTED]

[REDACTED]

### **2.11.6 Bath Ankylosing Spondylitis Disease Activity Index (BASDAI)**

The BASDAI will be completed at Visits 2 – 19. It consists of a 0 through 10 scale (0 being no problem and 10 being the worst problem, captured as a NRS), which is used to answer 6 questions pertaining to the 5 major symptoms of AS:

1. Fatigue
2. Spinal pain
3. Joint pain / swelling
4. Areas of localized tenderness (called enthesitis, or inflammation of tendons and ligaments)
5. Morning stiffness severity
6. Morning stiffness duration

To give each symptom equal weighting, the mean (average) of the two scores relating to morning stiffness is taken. The mean of questions 5 and 6 is added to the scores from questions 1-4. The resulting 0 to 50 score is divided by 5 to give a final 0 – 10 BASDAI score. Scores of 4 or greater suggest suboptimal control of disease, and subjects with scores of 4 or greater are usually good candidates for either a change in their medical therapy or for enrollment in clinical studies evaluating new drug therapies directed at AS. BASDAI is a quick and simple index taking between 30 seconds and 2 minutes to complete.

At least 4 questions should be non-missing to calculate the BASDAI score. Otherwise, BASDAI score will be missing (Haywood et al., 2002). If both Q5 and Q6 are missing or one of Q1 to

Q4 is missing, the total sum should be divided by 4 instead of 5. If two of Q1 to Q4 are missing and both Q5 and Q6 are not missing, the sum should be divided by 3.

BASDAI50 response is defined as at least a 50% improvement (decrease) in total BASDAI score, as compared to the baseline total BASDAI score.

Note: BASDAI is only assessed at Screening Visit 1 for TNF inhibitor inadequate responders currently on a TNF inhibitor and prior to discontinuation/washout.

### 2.11.7 ASAS Health Index (ASAS-HI)

The ASAS health index is a linear composite measure and contains 17 items (dichotomous response option: “I agree” and “I do not agree”).

Each statement on the ASAS health index is given a score of 1 = I agree OR 0 = I do not agree. All item scores are summed up to give a total score that ranges from 0 (good functioning) to 17 (poor functioning). Items No 7 and 8 are not applicable for all patients. For those patients who ticked the response “not applicable”, the sum score is analyzed based on n=16 or n=15, respectively.

A total score can be analyzed if no more than 20% of the data are missing. The total score is calculated as follows for respondents with one to a maximum of 3 missing responses:

$$\text{sumscore} = \frac{x}{17 - m} \times 17$$

x = Item summation score

m = Number of missing items

[figure not shown]
Cases with more than 3 missing responses cannot be allocated a total score.

## **2.12 Biomarkers**

Not Applicable.

### 2.13.2 Functional Assessment of Chronic Illness Therapy – Fatigue (FACIT-Fatigue)

The FACIT-Fatigue© is a 13-item questionnaire that assesses self-reported fatigue and its impact upon daily activities and function. The purpose of FACIT-Fatigue in this study is to assess the impact of fatigue on patients with AS. Subjects respond to each item on a 5-point Likert-type scale (0 = not at all; 1 = a little bit; 2 = somewhat; 3 = quite a bit; 4 = very much) based on their experience of fatigue during the past 2 weeks. The scale score is computed by summing the item scores, after reversing those items that are worded in the negative direction. Numbering the questions from 1 to 13, it is evident that questions 7 and 8 are worded in the positive direction (4 indicates a desirable response) and all other questions are worded in the negative directions (4 indicates an undesirable response). Thus, it is necessary to reverse the responses for all questions except questions 7 and 8 (i.e. original response of 0 gets mapped to 4, 1=3, 2=2, 3=1, and 4=0) for scoring purposes.

When there are missing item scores, the scale score will be computed by summing the non-missing item scores, multiplying by 13 (the total number of items in the scale) and dividing by the number of non-missing items (i.e., normalizing the results). The latter rule will be applied only when at least half of the items (seven or more) are non-missing.

FACIT-Fatigue scale score range from 0 to 52, where higher scores represent less fatigue (Cella et al., 2004).

[REDACTED]

[REDACTED]

[REDACTED]

- [REDACTED]
- [REDACTED]
- [REDACTED]

[REDACTED]

[REDACTED]

[REDACTED]

[REDACTED]

[REDACTED]

[REDACTED]

[REDACTED]

[REDACTED]

[REDACTED]

[REDACTED]

[REDACTED]

[REDACTED]

[REDACTED]

[REDACTED]

[Redacted text block]

e.

## 2.14 Interim analysis

No interim analysis is planned.

## 3 Sample size calculation

The sample size was calculated based on the primary efficacy variable (i.e., ASDAS inactive disease response) at Week 52 for the Full Analysis Set. The expected ASDAS inactive disease response rates for secukinumab 300 mg and 150 mg treatment groups at Week 52 are 20% and 10%, respectively (corresponding to an odds ratio of 2.25), partly based on results from AIN457F2310 (MEASURE 2) study. With approximately 97 patients in each treatment group (total of 194 randomized patients), one will be able to estimate the difference between ASDAS inactive disease response rates of the two treatment groups at Week 52 with a “margin of error” (half-width of confidence interval) of 10% (corresponding to a standard error of 5%) for a two-sided 95% confidence interval (Julious and Patterson, 2004; nQuery Advisor 7.0).

It is expected that the study will need to enroll approximately 270 patients for the 16-week open-label period, to randomize approximately 194 patients who do not achieve ASDAS inactive disease status at Week 16 (inadequate responders). This assumes that 10% of the 270 enrolled patients will discontinue during the 16-week open-label period; among the remaining enrolled patients, it is assumed that approximately 10% will be responders, 80% will be inadequate responders, and 10% will be non-responders.

## 4 Change to protocol specified analyses

For (continuous) secondary efficacy variables 2, 7, and 8 ([Section 2.7.1](#)), multiple imputation will not be performed as an additional analysis

For secondary efficacy variables 2, 7, and 8 MMRM will be used for analysis instead of ANCOVA. LOCF will not be used to handle missing data for these variables.

For safety analyses in Treatment Period 1, definition of Enrolled Set will be updated to include patients who received the open-label secukinumab 150 mg.

Randomized Set was deleted.

## 5 Appendix

This section will be used later for drafting CSR Appendix 16.1.9.

## 5.1 Imputation rules

### 5.1.1 Study drug

Not applicable.

### 5.1.2 AE date imputation

The following table explains the notation used in the logic matrix. Please note that missing start dates will not be imputed.

	Day	Month	Year
Partial Adverse Event Start Date	Not used	MON	YYYY
Treatment Start Date (TRTSTD)	Not used	TRTM	TRTY

The following matrix explains the logic behind the imputation.

	MON MISSIN	MON < TRTM	MON = TRTM	MON > TRTM
YYYY MISSIN	NC Uncertain	N C	N C	N C
YYYY < TRTY	(D) Before Treatment Start	(C )	(C )	(C )
YYYY = TRTY	(B) Uncertain	(C ) Before Treatment	(A ) Uncertain	(A ) After Treatment
YYYY > TRTY	(E) After Treatment Start	(A ) After Treatment	(A ) After Treatment	(A ) After Treatment

The following table is the legend to the logic matrix.

If AE end date is complete and AE end date < Treatment start date or AE end date is partial and AE imputed end date < Treatment start date, then AE start reference = min (informed consent date, earliest visit date from SV) Else if AE end date is partial, AE end date > = Treatment start date or AE is ongoing, then AE start reference = treatment start date.

Relationship	Time imputation
Before AE start reference	Partial date indicates AE start date prior to AE start
After AE start reference	Partial date indicates AE start date after AE start
Uncertain	Partial date insufficient to determine relationship of AE start date to AE start
Imputation Calculation	

NC/Blank	No convention	
(A)	MAX( 01MONYYYY, AE start reference+1 day)	
(B)	AE start reference+1	
(C)	15MONYYYY	
(D)	01JULYYYY	
(E)	01JANYYYY	
Complete date	No date imputation	If time is captured for the study Case1: if AE start date is not equal to AE start reference then do the following:

Relationship	Time imputation
	If minutes missing then AESTMF = M and time is imputed to hh:00 If minutes missing then AESTMF = H and time is imputed to 00:00 Case2: if AE start date = AE start reference then AESTMF = H and time is imputed to treatment start time + 1 hour

### Adverse Event End Date Imputation

Imputed date = date part of original date, if complete date

Imputed date = min (completion/discontinuation visit date, DEC 31, date of death), if month is missing

Imputed date = min (completion/discontinuation visit date, last day of the month, date of death), if day is missing

### Adverse Event End Time Imputation

If the AE end date is complete and time is captured in the study then:

**Case 1.** if AE end date is not equal to Treatment end date, then do the following:

if minutes missing then time is imputed to hh:00 if time missing then time is imputed to 00:00

**Case 2:** if AE end date = Treatment end date then time is imputed to treatment end time

If the AE end date is partial then end time is imputed to 00:00.

### Imputed Date Flag

If year of the imputed date is not equal to YYYY then date flag = Y

else if month of the imputed date is not equal to MON then date flag = M

else if day of the imputed date is not equal to day of original date then date\_flag = D

else date flag = null

### Imputed Time Flag

If hours of the imputed time is not equal to hours of original time then time flag = H  
 else if minutes of the imputed time is not equal to minutes of original time then time flag = M  
 else time flag = null.

### 5.1.3 Concomitant medication date imputation

This algorithm is used when *event* is the partial start date of the concomitant medication. The following table explains the notation used in the logic matrix. Please note that **missing start dates** will not be imputed.

	Day		Year
Partial CM Start Date	Not used	MON	YYYY
Treatment Start Date	Not used	TRTM	TRTY

The following matrix explains the logic behind the imputation.

	MON MISSING	MON < TRTM	MON = TRTM	MON > TRTM
YYYY MISSING	(C2) Uncertain	(C1) Uncertain	(C1) Uncertain	(C1) Uncertain
YYYY < TRTY	(D) Before Treatment Start	(A) Before Treatment Start	(A) Before Treatment Start	(A) Before Treatment Start
YYYY = TRTY	(C2) Uncertain	(A) Before Treatment Start	(C1) Uncertain	(B) After Treatment Start
YYYY > TRTY	(E) After Treatment Start	(B) After Treatment Start	(B) After Treatment Start	(B) After Treatment Start

The following table is the legend to the logic matrix.

Relationship	
Before Treatment Start	Partial date indicates CMD start date prior to Treatment Start Date
After Treatment Start	Partial date indicates CMD start date after Treatment Start Date
Uncertain	Partial date insufficient to determine relationship of CMD start date relative to Treatment Start Date
Imputation Calculation	
(A)	15MONYYYY
(B)	01MONYYYY
(C1 or C2)	IF relative reference start = before treatment start THEN TRTSDT-1 ELSE IF relative reference start = '' THEN TRTSDT+1
(D)	01JULYYYY
(E)	01JANYYYY

### **Concomitant Medication End Date Imputation**

If not ongoing then -

Imputed date = date part of CMENDTC, [if complete date](#)

Imputed date = min(completion/discontinuation visit date, DEC 31) , if month is missing, [\(C2, D, E\)](#)

Imputed date = min(completion/discontinuation visit date, last day of the Month) , if day is missing. [\(A, B, C1\)](#)

### **Concomitant Medication Date Flag**

If not a complete date then

Y - If year of the imputed date is not equal to YYYY else M – If month of the imputed date is not equal to MON else D.

#### **5.1.3.1 Prior therapies date imputation**

Same as above.

#### **5.1.3.2 Post therapies date imputation**

Same as above.

#### **5.1.3.3 Other imputations**

Same as above.

#### **5.1.4 Medical history date of diagnosis imputation**

Completely missing dates and partially missing end dates will not be imputed. Partial dates of diagnosis will be compared to the treatment start date.

- If DIAG year < study treatment start date year and DIAG month is missing, the imputed DIAG date is set to the mid-year point (01JULYYYY).
- Else if DIAG month is not missing, the imputed DIAG date is set to the mid-month point (15MONYYYY).
- If DIAG year = study treatment start date year and (DIAG month is missing OR DIAG month is equal to study treatment start month), the imputed DIAG date is set to one day before study treatment start date.

### **5.2 AEs coding/grading**

Not applicable.

### 5.3 Laboratory parameters derivations

Not applicable.

### 5.4 Statistical models

#### 5.4.1 Primary analysis

The primary analysis will be performed comparing treatments with respect to the primary efficacy variable in a logistic regression model with treatment, TNF-alpha inhibitor (naive, inadequate responder) and baseline body weight as explanatory variables.

```
Proc logistic data=aaa;  
Class TRT TNF/ param=glm;  
Model AVAL= TRT TNF base_weight;  
Lsmeans TRT / diff cl exp;  
Ods output diffs=lsd_diff;  
Run;
```

Where TRT = treatment group  
TNF = TNF-alpha inhibitor (naive, inadequate responder)  
Base\_weight = baseline body weight

Logistic regression will be applied to response variables at each visit.

In cases where separation is a concern, e.g., 0% response in one treatment group, an exact logistic regression model will be applied.

```
Proc logistic data=aaa exactly;  
Class TRT TNF / param=glm;  
Model AVAL = TRT TNF base_weight;  
Exact TRT / estimate;  
Ods output exactoddsratio=exactoddsratio;  
Run;
```

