### **2.5.2 Statistical hypothesis, model, and method of analysis**

Let  $\pi_j$  denote the probability of an ASDAS inactive disease at Week 52 for treatment group  $j$ ,  $j = 1, 2$ , where 1 and 2 correspond to secukinumab 150 mg and secukinumab 300 mg, respectively. Accordingly,  $\pi_j/(1 - \pi_j)$  is the odds for treatment group  $j$ ,  $j = 1, 2$ .

The primary efficacy variable will be analyzed at each time point until Week 52 using a logistic regression model with treatment, TNF-alpha inhibitor status (naive, inadequate responder), and Week 16 body weight as explanatory variables (Stokes, Davis, and Koch, 2012). The odds ratios and 95% confidence intervals for the odds ratios will be reported, based on the fitted model.

Number and percentages for ASDAS inactive disease response will also be reported for each treatment group, by TNF-alpha inhibitor status (naive, inadequate responder) by visit. A line plot for ASDAS inactive disease responders (%) from Week 16 to Week 52 will be presented. A similar line plot will be presented by TNF-alpha inhibitor status.

A line plot for ASDAS inactive disease responders (%) over entire treatment period (from Week 1 to Week 52) will be presented. A similar line plot will be presented by TNF-alpha inhibitor status.

Also, number and percentages for the patients with ASDAS inactive disease response in Treatment Period 1 who entered Treatment Period 2 will be provided based on the below criteria:

- Patients receiving 150mg (open label) (Enrolled Set)
- Patients receiving randomized 300mg and 150mg (Randomized Set)
- Patients who are responders (Responder Set)
- Patients who are nonresponders (Nonresponder Set)

In addition, the above analysis will be done by TNF-alpha inhibitor status and by visit.

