    tables <response> / binomial (level=2 cl=wilson correct) ;
    ods output BinomialProp=imp_bpr;
run;
```

Transpose the dataset for subsequent use with PROC MIANALYZE.

```
proc transpose data=imp_bpr out=imp_trs(drop=_name_);  
  by treat visit _imputation_ ;  
  var nvalue1; id name1; idlabel label1;  
run;
```

Apply LOGIT transformation:  $y = \log(p/(1-p))$  and std. err. transformation:  $\langle \text{new se} \rangle = \text{se}/(p*(1-p))$

```
data logit;  
  set imp_trs(rename=( _bin_ =p e_bin=se));  
  by treat visit _imputation_ ;  
  lmean=log(p/(1-p));  
  lse=se/(p*(1-p));  
run;
```

The transformed binomial proportion estimates and standard errors are combined by applying Rubin's rules for multiple imputed data sets.

```
proc mianalyze data=logit;  
  by treat visit ;  
  modeleffects lmean;  
  stderr lse;  
  ods output ParameterEstimates=logitres;  
run;
```

The combined data should be transformed back using the following formula:  $p = 1/(1 + \exp(-y))$

```
data miexpres;  
  set logitres;  
  by treat visit ;  
  resti = 1/(1+exp(-estimate));  
  rlow = 1/(1+exp(-lclmean));  
  rupp = 1/(1+exp(-uclmean));  
run;
```

If all responses are imputed the same as 0 (or 1) for all imputation datasets for a specific treatment or subgroup, then the between-imputation-variation will be zero. The combined final response rate for the specific treatment would be presented as seen in any of the imputed datasets together with 95% confidence interval from Wilson's method (as obtained from PROC FREQ).

The following steps will be performed to handle special cases:

- If after imputation all responses (observed + imputed) are the same either 0 or 1 for all imputation datasets for a specific treatment, it will not be possible to perform a logit transformation and the response rate (0% or 100%) for these cases will be presented together with the 95% CI from Wilson's method (as obtained from PROC FREQ).
- If after imputation the average response rate is the same across all imputed datasets (but not 0 or 1), there is no between-dataset variation and Rubin's rules cannot be applied. Instead the average response will be used with 95% CI from Wilson's method (as obtained from PROC FREQ).

The odds ratio will be derived using GENMOD for each imputation, then combined using Rubin's rules again.

```
proc genmod data = acr20_mi descending;
    by avisitn _imputation_ ;
    class trt_ TNFRESN ;
    model aval = trt_ TNFRESN weight / link=logit dist=bin;

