    lsmeans trt_ / diff;
    estimate 'AIN457 150 mg vs AIN457 300 mg' trt_ 1 -1;
    estimate 'AIN457 150mg mg vs Placebo' trt_ 0 1 -1;
    ods output Estimates=imp_est;

run;

proc mianalyze data=imp_est;
    by avisitn trt_ ;
    modeleffects LBetaEstimate;
    stderr StdErr;
    ods output ParameterEstimates=_res;

run;
```

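### The primary and exact logistic programs name no response event and, under 0/1 coding, model non-response, while the multiple-imputation program models response

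*SAP*

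**What the plan says.** - **Text.** SAP 2.5.2 lets pi_j "denote the probability of an ASDAS inactive disease at Week 52 for treatment group" j, with 150 mg numbered 1 and 300 mg numbered 2, and forms the odds from it. The odds are therefore odds of response. SAP 3 gives expected rates for 300 mg and 150 mg that "are 20% and 10%, respectively (corresponding to an odds ratio of 2.25"), which is the response odds ratio for 300 mg relative to 150 mg.
- **Primary program (SAP 5.4.1).** The model line is "Model AVAL= TRT TNF base_weight". It has no event option, and the procedure line has no descending option. The treatment comparison is an exponentiated least-squares-means difference without a label. The exact program for separation repeats the model line, again without an event level.
- **Multiple-imputation program (same section).** It opens with "proc genmod data = acr20_mi descending" and takes the contrast "estimate 'AIN457 150 mg vs AIN457 300 mg' trt_ 1 -1". A further line reads "estimate 'AIN457 150mg mg vs Placebo' trt_ 0 1 -1".
- **Reach.** SAP 5.4.3 sends the binary secondary variables to the same logistic code. SAP 5 says the appendix will be used in drafting CSR Appendix 16.1.9.

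**The concern.** The model-based odds ratio is the main reported comparison for the primary endpoint, and the imputation analysis is meant to stand beside it. The text settles that the odds are of response, but a programmer who follows the code gets odds of the opposite event in the primary and exact programs and odds of response in the imputation program. No sentence fixes the coding of AVAL, the order of the treatment levels or the direction in which the odds ratio is reported. A primary row headed 150 versus 300 and read as response would appear to favour 150 mg, while the imputation row would favour 300 mg. A check on size alone would not reveal this, because 2.25 is also the planned value.

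**Working it through.** **Inputs.** Planned response rates are 20% (300 mg) and 10% (150 mg), from SAP 3. Arm size: "With approximately 97 patients in each treatment group (total of 194 randomized patients"). Precision: "half-width of confidence interval) of 10% (corresponding to a standard error of 5%) for a two-sided 95% confidence interval". Treatment numbering is from SAP 2.5.2 and the programs are from SAP 5.4.1.

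**Step 1: reproduce the plan.**
- Response odds ratio, 300 versus 150: (0.20/0.80)/(0.10/0.90) = 0.25/0.1111 = 2.25, as stated.
- Sample size per arm: 1.96² × (0.20×0.80 + 0.10×0.90)/0.10² = 96.04, rounded up to 97. At 97 the half-width is 0.0995. Both agree with the plan.

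**Step 2: which event each program models.** This needs one fact from outside the documents, the SAS default: without an event or descending option, the first ordered level is modelled. The primary and exact programs then model the lower level of AVAL, and the imputation program models the higher. They model opposite events under any coding they share. Which one is non-response depends on the coding. The imputation text speaks of responses imputed as 0 or 1 and takes the response rate from the second level, so response is 1 and the primary program models non-response.

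**Step 3: odds ratios at the planning rates, 150 mg sorting first in both programs.**
- Primary, non-response, 150 versus 300: (0.90/0.10)/(0.80/0.20) = 9/4 = 2.25.
- Imputation, response, 150 versus 300: 0.1111/0.25 = 0.444.
- Expected counts at 97 per arm are 9.7 and 87.3 (150 mg), and 19.4 and 77.6 (300 mg). SE of the log odds ratio = √(1/9.7 + 1/87.3 + 1/19.4 + 1/77.6) = 0.423. The 95% intervals are 0.98 to 5.16 for 2.25 and 0.19 to 1.02 for 0.444.
- A covariate-adjusted fit of both events to one simulated data set gave 2.490 and 0.402, product 1.00.

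**Step 4: dependence on level order.** The programs use different treatment variables (TRT and trt_), and neither ordering is given.

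| First level, primary | First level, imputation | Primary (non-response) | Imputation (response) |
|---|---|---|---|
| 150 | 150 | 150 vs 300: 2.25 | 150 vs 300: 0.444 |
| 300 | 300 | 300 vs 150: 0.444 | 300 vs 150: 2.25 |
| 300 | 150 | 300 vs 150: 0.444 | 150 vs 300: 0.444 |
| 150 | 300 | 150 vs 300: 2.25 | 300 vs 150: 2.25 |

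In rows two and four the imputation contrast would also carry the wrong label.

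**Step 5: dependence on missing data.** The primary analysis counts discontinued patients as non-responders (SAP 2.5.3), whereas the imputation assumes missing at random. The plan gives no dropout rate for Treatment Period 2, so assume 10% to 20% per arm, unrelated to response.
- 10% on 150 mg and 20% on 300 mg: observed rates 0.09 and 0.16, primary figure (0.91/0.09)/(0.84/0.16) = 1.93.
- 20% on 150 mg and 10% on 300 mg: observed rates 0.08 and 0.18, primary figure (0.92/0.08)/(0.82/0.18) = 2.52.
- The imputation figure stays at 0.444. The products are 0.86 and 1.12, so the values are no longer reciprocal but still lie on opposite sides of 1.

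**The case against.** The strongest reply is that no number is shown to be wrong. Non-response odds for 150 versus 300 are identical to response odds for 300 versus 150, interval included, so the primary program returns the planned 2.25. The imputation row, at its own label and with 150 mg first, correctly returns 0.444. SAP 2.5.2 already defines the odds, and response percentages by arm and a confidence interval for the difference in proportions (SAP 2.5.4) would expose a reversal. The code is visibly a template and would be edited before use.

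Most of this stands. A reader might infer that the primary result will be reported as favouring 150 mg. The SAP does not say so: only the imputation contrast carries a label, and the primary comparison has none. A reader might also infer that the two odds ratios must come out as reciprocals. Steps 4 and 5 show that this needs the same level order and the same data in both programs.

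The reply does not remove the mismatch. The text defines odds of response, and the primary and exact programs, run as written, give odds of the other event. That the number agrees depends on an unstated sort order. The appendix is intended for the study report, so calling it a template is a reason to correct it.

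**Conclusion.** The point holds as a specification gap that should be closed, not as an error in the primary estimate. The primary and exact programs model non-response and the imputation program models response, against a text that defines the odds on response. At the planning rates, with 150 mg first in both, the 150-versus-300 rows read about 2.25 and about 0.44. This rests on three assumptions: 0/1 coding of AVAL (implied by the imputation text, not stated for the primary program), the SAS default for the modelled level, and 150 mg sorting before 300 mg. The opposite events need only the default and a shared coding. The two specific values also need the level order and the planning rates. The same gap passes to the five binary secondary variables. The placebo contrast and the ACR20 data set name are template leftovers. They bias nothing, but they show that the block was not adapted to this two-arm comparison.

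**What to change.** - **Primary and exact programs:** write the response as `AVAL(event='1')` and state that 1 means response. The binary secondary analyses inherit the change.
- **All programs:** name 150 mg as the reference, for example `TRT(ref='150 mg')` or `diff=control('150 mg')`, matched to the level names in the data. Do not simply reverse the contrast coefficients, since that still relies on sort order.
- **Imputation program:** relabel the contrast as 300 mg versus 150 mg, delete the placebo contrast and correct the data set name.
- **Text:** add one sentence to SAP 2.5.2 stating that every odds ratio is for response, 300 mg relative to 150 mg.

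With these changes both programs give 2.25 at the planning rates. The cost is a few words of code and one sentence, with no change to design, data or model. Separately, SAP 2.5.2 adjusts for Week 16 body weight and SAP 5.4.1 for baseline body weight. That should be settled while the same model line is open.
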